4.5.4 CDAI Remission and Low Disease Activity

Remission is defined as a CDAI score of ≤ 2.8 . Low disease activity is defined as a CDAI score of ≤ 10 .

The frequency and percentage of patients achieving remission and low disease activity will be summarized by treatment arm at each post-baseline visit. A logistic regression model will be used to test the treatment difference of each LY dose versus placebo at each post-baseline visit with treatment group, baseline value, and previous RA therapy population as model covariates. NRI as described in Section 4.1 will be used to impute missing data for CDAI remission and low disease activity in patients who were Week 12 non-responders or who discontinued prior to Week 12.

The analyses for CDAI remission and CDAI LDA will be repeated for all visits in period 2. NRI as described in Section 4.1 will be used to impute missing data for CDAI in patients who were Week 24 non-responders or who discontinued prior to Week 24.

For participants who discontinue study intervention and/or receive rescue therapy, post-discontinuation or post-rescue observations will not be included.

4.5.5 MRI

Observed values at baseline and changes from baseline to Week 12 in synovitis, osteitis, combined inflammation (combination of synovitis and osteitis), bone erosion, cartilage loss (scored with the validated 9-point Cartilage Loss Scale) and total joint damage which were scored using Outcome Measures in Rheumatology Clinical Trials RA MRI scoring (RAMRIS) will be summarized by treatment arm and provided as listing.

Scale-adjusted scores for combined inflammation (osteitis score + $3 \times$ synovitis score) and total joint damage (erosion score + $2.5 \times$ cartilage loss score) were calculated. Synovitis is multiplied by 3 to adjust for the about 3-fold difference between the scales for synovitis (0–24) and for osteitis (0–75). The scale difference is also adjusted when computing total damage score (bone erosion scale ranges 0–250, cartilage loss ranges 0–100).

An ANCOVA model of change from baseline with treatment and previous RA therapy population included as fixed factors, and baseline value as a continuous covariate will be used to test the treatment difference of each LY dose versus placebo. Least squares mean (LSM), standard error, within-group p-value, and two-sided 95% confidence interval for change from baseline will be reported for each treatment arm. For the treatment difference of each LY dose versus placebo, the LSM difference, standard error, p-value, and two-sided 95% confidence interval will be reported.

The frequency and percentage of patients achieving 25% improvement on total synovitis score will be summarized by treatment arm at Week 12. A logistic regression model will be used to test the treatment difference of each LY dose versus placebo at Week 12 with treatment group, baseline value, and previous RA therapy population as model covariates. NRI as described in Section 4.1 will be used to impute missing data in patients who were Week 12 non-responders or who discontinued prior to Week 12.

For participants who discontinue study intervention and/or receive rescue therapy, post-discontinuation or post-rescue observations will not be included.

4.5.6 Disease Activity and PROs

Observed values at baseline and changes from baseline to Week 12 endpoint of disease activity score, PRO score, SF-36 domain score, the physical component score, the mental component

scores will be summarized by treatment arm and provided as listing. An MMRM model, as described in Section 4.3.2, will be used to test the treatment difference of each LY dose versus placebo in change from baseline to Week 12 endpoint.

The frequency and percentage of patients achieving desired response will be summarized by treatment arm at each post-baseline visit. A logistic regression model will be used to test the treatment difference of each LY dose versus placebo at each post-baseline visit with treatment group, baseline value, and previous RA therapy population as model covariates. NRI as described in Section 4.1 will be used to impute missing data for CDAI remission and low disease activity in patients who were Week 12 non-responders or who discontinued prior to Week 12.

For participants who discontinue study intervention and/or receive rescue therapy, post-discontinuation or post-rescue observations will not be included.

4.5.7 Analyses in Period 2

Observed values at baseline and changes from Week 12 to Week 24 endpoint of DAS28-CRP, DAS28-ESR, HAQ-DI, SDAI, CDAI, tender joint count, swollen joint count, Patient's Global Assessment of Arthritis Pain (VAS), Patient's Global Assessment of Disease Activity (PaGADA_VAS), Physician's Global Assessment of Disease Activity (PhGADA_VAS) will be summarized by treatment arm. An MMRM model, as described in Section 4.3.2, will be used to test the treatment difference of each LY dose versus placebo in change from Week 12 to Week 24 endpoint.

The frequency and percentage of patients achieving desired responses on ACR20/50/70 at Week 14 and maintain till Week 24 will be summarized by treatment arm at each period 2 visit. A logistic regression model will be used to test the treatment difference of each LY dose versus placebo at each period 2 visit with treatment group, baseline value at double-blind treatment period, and previous RA therapy population as model covariates. NRI as described in Section 4.1 will be used to impute missing data in patients who were Week 24 non-responders or who discontinued prior to Week 23.

For participants who discontinue study intervention and/or receive rescue therapy, post-discontinuation or post-rescue observations will not be included.

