1.2. Study Design

This is a Phase 2, proof-of-concept, placebo-controlled, double-blind, randomized study in adult participants with moderately to severely active RA who have had an inadequate response to csDMARDs, or to bDMARDs/tsDMARDs. Participants will be administered LY3462817 or placebo IV Q4W.

Screening Period (Visit 1, Days -42 to -1)

Participants will sign the informed consent document(s) at Visit 1, prior to completion of any procedures. Participants will be evaluated for study eligibility ≤ 42 days prior to the baseline visit (Visit 2).

Period 1: Double-blind Treatment (Visits 2 to 6; 12 weeks)

At the baseline visit (Visit 2), participants who fulfill the eligibility criteria will be randomized to receive LY3462817 700 mg, LY3462817 300 mg, or placebo in an allocation ratio of 2:1:1. The double-blind treatment period will establish the clinical efficacy and safety of LY3462817. The study will be evaluated for the primary objective at the end of the double-blind treatment period.

Period 2 (Visits 6 to 10; 12 weeks)

In Period 2, all subjects will receive LY3462817 to assess safety and tolerability data and explore clinical activity with additional dosing. At Week 14, participants will be evaluated for clinical benefit.

Posttreatment Safety Follow-up Period (Visits V801 and 802; 12 weeks)

Following Period 2, participants will be followed posttreatment for 12 weeks to assess safety, study drug exposure, and clinical disease activity measures.

2. Statistical Hypotheses

For the primary estimand with primary endpoint, change from baseline to week 12 in DAS28-CRP, the following 2 (confirmatory) 1-sided hypotheses are planned to be tested for LY3462817 700 mg versus placebo. Let the mean treatment difference be defined as $\mu = (\text{LY3462817 700 mg} - \text{placebo})$.

$H_0: \mu \geq 0.0$ against $H_a: \mu < 0.0$

Operationally the hypotheses will be evaluated by 2-sided tests.

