4.5. Tertiary/Exploratory Endpoints/Estimands Analysis

4.5.1 DAS28-CRP Remission and Low Disease Activity

Remission is defined as a DAS28-CRP score of <2.6. Low disease activity is defined as a DAS28-CRP score of ≤ 3.2 .

The frequency and percentage of patients achieving remission and low disease activity will be summarized by treatment arm at each post-baseline visit. A logistic regression model will be used

to test the treatment difference of each LY dose versus placebo at each post-baseline visit with treatment group, baseline value, and previous RA therapy population as model covariates. NRI as described in Section 4.1 will be used to impute missing data for DAS28-CRP remission and low disease activity in patients who were Week 12 non-responders or who discontinued prior to Week 12.

The analyses for DAS28-CRP remission and DAS28-CRP LDA will be repeated for all visits in period 2. NRI as described in Section 4.1 will be used to impute missing data for DAS28-ESR in patients who were Week 24 non-responders or who discontinued prior to Week 24.

For participants who discontinue study intervention and/or receive rescue therapy, post-discontinuation or post-rescue observations will not be included.

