4.5.2 DAS28-ESR Remission and Low Disease Activity

Remission is defined as a DAS28-ESR score of <2.6 . Low disease activity is defined as a DAS28-ESR score of ≤ 3.2 .

The frequency and percentage of patients achieving remission and low disease activity will be summarized by treatment arm at each post-baseline visit in Double-blind Treatment Period. A logistic regression model will be used to test the treatment difference of each LY dose versus placebo at each post-baseline visit with treatment group, baseline value, and previous RA therapy population as model covariates. NRI as described in Section 4.1 will be used to impute missing data for DAS28-ESR remission and low disease activity in patients who were Week 12 non-responders or who discontinued prior to Week 12.

The analyses for DAS28-ESR remission and DAS28-ESR LDA will be repeated for all visits in period 2. NRI as described in Section 4.1 will be used to impute missing data for DAS28-ESR in patients who were Week 24 non-responders or who discontinued prior to Week 24.

For participants who discontinue study intervention and/or receive rescue therapy, post-discontinuation or post-rescue observations will not be included.

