4.5.3 SDAI Remission and Low Disease Activity

Remission is defined as a SDAI score of ≤ 3.3 . Low disease activity is defined as a SDAI score of ≤ 11 .

The frequency and percentage of patients achieving remission and low disease activity will be summarized by treatment arm at each post-baseline visit. A logistic regression model will be used to test the treatment difference of each LY dose versus placebo at each post-baseline visit with treatment group, baseline value, and previous RA therapy population as model covariates. NRI as described in Section 4.1 will be used to impute missing data for SDAI remission and low disease activity in patients who were Week 12 non-responders or who discontinued prior to Week 12.

The analyses for SDAI remission and SDAI LDA will be repeated for all visits in period 2. NRI as described in Section 4.1 will be used to impute missing data for SDAI in patients who were Week 24 non-responders or who discontinued prior to Week 24.

For participants who discontinue study intervention and/or receive rescue therapy, post-discontinuation or post-rescue observations will not be included.

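### SAP 4.5.1 to 4.5.4 and 4.5.7 test each LY dose against placebo at Weeks 16 to 24, when nobody is planned to be on placebo

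*SAP*

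**What the plan says.** SAP 4.5.7 covers ten continuous measures and ACR20/50/70 in Period 2. For the continuous measures an MMRM will "test the treatment difference of each LY dose versus placebo in change from Week 12 to Week 24 endpoint". For ACR response a logistic model will "test the treatment difference of each LY dose versus placebo at each period 2 visit".

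SAP 4.5.1 to 4.5.4 describe logistic tests of each LY dose versus placebo for remission and low disease activity (LDA), then extend them to Period 2. For DAS28-CRP the wording is "The analyses for DAS28-CRP remission and DAS28-CRP LDA will be repeated for all visits in period 2"; DAS28-ESR, SDAI and CDAI have the same sentence. For missing data these sections apply nonresponder imputation (NRI) to anyone who discontinued before Week 24 (before Week 23 in 4.5.7).

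Each section ends with the same exclusion: "For participants who discontinue study intervention and/or receive rescue therapy, post-discontinuation or post-rescue observations will not be included".

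The documents give two accounts of what placebo participants receive in Period 2. Protocol 4.1 continues infusions only for participants randomized to LY who reach CDAI of 10 or less at Week 14. Everyone else stops infusions and should receive SOC, and protocol 6.5.3 repeats this for the placebo arm. SAP 1.2 says: "In Period 2, all subjects will receive LY3462817 to assess safety and tolerability data and explore clinical activity with additional dosing". SAP 4.6.1 nevertheless limits Period 2 exposure summaries to those still on one of the LY doses, which does not fit SAP 1.2.

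**The concern.** A test of LY versus placebo needs observed placebo outcomes, or a stated estimand that says what stands in for them. After Week 14 the plan has neither. The protocol's estimand table is limited to the double-blind period, and the SAP's estimands are all at Week 12.

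The SAP also does not say whether the planned Week 14 move to SOC is a discontinuation, a rescue or neither. That choice decides whether the contrast can be computed and what it means, and as written it falls to whoever programs the analysis. Durability to Week 24 is a listed exploratory objective, so these outputs will be read. A placebo response rate of zero produced by an imputation rule, or an LY-versus-SOC contrast under a placebo label, could be mistaken for evidence of sustained benefit.

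**Working it through.** The plan gives no figure for any Period 2 comparison. Its one power statement is for Week 12 and reproduces: difference 1.80 − 0.75 = 1.05, SD 1.25, 40 versus 20 participants. The noncentrality is 1.05 / (1.25 × √(1/40 + 1/20)) = 3.07 on 58 df, and two-sided power at 0.05 is 0.855, which agrees with the stated figure of more than 80%. Nothing below changes that.

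**1. Who is on placebo at Weeks 16, 20 and 24**

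| Source | Placebo arm after Week 14 | Planned on placebo |
|---|---|---|
| Protocol 4.1 and 6.5.3 | Infusions stop, SOC | 0 of about 20 |
| SAP 1.2 | LY | 0 of about 20 |

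The dosing comment in the Schedule of Activities ties infusions at Weeks 16 to 24 to LDA at Week 14 without naming an arm. Read alone, it could keep a placebo participant on infusions. Protocol 4.1 and 6.5.3 are more specific and exclude that.

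**2. Does the Week 14 move count as discontinuation or rescue?** The text points both ways.
- For: the general NRI rule in SAP 4.1 covers permanent stopping before the end of the treatment period, and SAP 4.1 defines the Treatment Period as Period 1 plus Period 2.
- Against: protocol 7.1.2 describes permanent discontinuation as rare, and protocol 6.5.1 applies the concomitant-therapy rules in Period 2 only to those still on LY.

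**3. Reading A: it counts. Continuous measures.** Take the visits after Week 12 at which most measures are collected: Weeks 14, 16, 20 and 24. The SAP 4.3.2 model has 1 intercept + 2 treatment + 3 visit + 6 treatment-by-visit + 1 stratum + 1 baseline = 14 columns. This is equivalent to 3 arms × 4 visits = 12 cell means plus 2 covariates. Assume some LY continuers in each dose arm.
- Placebo rows removed after Week 14: 3 of 12 cells are empty, rank 9 + 2 = 11 of 14. The LY-placebo contrast is estimable at Week 14 and at none of Weeks 16, 20 and 24.
- SAP 4.3.2 also excludes data from the point of discontinuation itself. If that removes Week 14, 4 cells are empty, rank 8 + 2 = 10 of 14, and no contrast is estimable at any of the four visits.
- DAS28-ESR is collected in Period 2 only at Week 24: 3 cells + 2 covariates = 5 columns, rank 4 without placebo, and neither dose contrast is estimable.

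**4. Reading A: binary measures.** NRI sets placebo to 0/20. The placebo odds are 0/20 = 0, so the log odds ratio for any LY arm with at least one responder has no finite maximum-likelihood value (separation). With an assumed 10/40 responders on 700 mg, the unadjusted fit gave log odds ratios of 5.1, 10.1, 21.2 and 23.4 after 5, 10, 20 and 35 iterations and never converged. The direction is also fixed: LY continuers can still respond, while a placebo participant in LDA at Week 14 is moved to SOC and scored a nonresponder.

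**5. Reading B: it does not count, or SAP 1.2 stands.** All rows stay, the ranks are 14 of 14 and 5 of 5, and every contrast can be computed. Under the protocol it compares LY followed by LY or SOC (according to Week 14 response) with placebo followed by SOC. Under SAP 1.2 it compares LY throughout with placebo followed by LY. Neither is LY versus placebo.

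**6. Number of tests, two doses each**
- 4.5.1, 4.5.3, 4.5.4: 3 measures × 2 states × 3 visits × 2 doses = 36
- 4.5.2: 2 states × 1 visit × 2 doses = 4
- 4.5.7 continuous: 10 measures × 2 doses = 20
- 4.5.7 ACR: 3 levels × 3 visits × 2 doses = 18

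Total 36 + 4 + 20 + 18 = 78. This is one drafting fault repeated across rows, not 78 separate faults.

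**The case against.** The best defence is that these are exploratory tests with no multiplicity adjustment and no stated decision attached. The planned interim efficacy rule concerns Period 1, and the primary lock follows the double-blind period. That stands, and it limits the severity.

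A second defence is that the full analysis set groups participants by planned intervention, so a Week 24 comparison by randomized arm is a legitimate comparison of strategies. That also stands, provided it is labelled so. The fault is the placebo label and the handling of the Week 14 move, not the use of randomized arms.

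A reader might infer more than the documents support:
- **That the Week 12 responder analyses fail too.** Read literally, the general NRI rule has no visit limit and would make every placebo participant a Week 12 nonresponder. SAP 4.4.1.2.1 restricts its imputation to Week 12 nonresponders and those who discontinued before Week 12, so this reading is not supported.
- **That the Week 14 comparison is invalid because Week 14 lies in Period 2.** Under the protocol the Week 12 infusion is still randomized treatment, so a Week 14 contrast remains LY versus placebo if the data are kept.
- **That the binary tests would come out significant by rule.** The documents give no Period 2 responder counts, and the SAP does not name the test statistic for the logistic model. Under separation that choice decides the p-value, so no p-value is claimed here.
- **That the SAP was written to an outdated protocol.** It cites the protocol dated 05AUG2020, while the supplied protocol mentions a decision of 08 September 2020. The earlier protocol is not available, and carried-over template text is an equally possible cause.

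**Conclusion.** The tests are wrong as written and should be fixed. On either account of Period 2, nobody is planned to be on placebo at Weeks 16, 20 or 24, so none of these outputs can support a statement about LY versus placebo. If the Week 14 move counts as discontinuation or rescue, the continuous contrast cannot be estimated, and the placebo response rate is zero by rule, which biases the binary comparison toward LY. Otherwise the contrast is computable but estimates a difference between treatment sequences.

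This rests on the protocol's planned course at Week 14, about 20 placebo participants, some LY continuers in each dose arm, and the Schedule of Activities visits. It does not depend on settling which reading of the Week 14 move is right. The scope is exploratory: the Week 12 primary and secondary analyses are not at issue.

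**What to change.** 1. Reconcile SAP 1.2 and 4.6.1 with protocol 4.1 and 6.5.3, and cite the current protocol version in the SAP.
2. Remove the LY-versus-placebo tests at Weeks 16, 20 and 24 from 4.5.1, 4.5.3, 4.5.4 and the 4.5.7 ACR analysis, and at Week 24 from 4.5.2. Remove the 4.5.7 MMRM test of change from Week 12 to Week 24.
3. If the protocol's Period 2 stands, a Week 14 comparison with placebo may stay for DAS28-CRP, SDAI, CDAI and ACR20/50/70, whose components are all scheduled at that visit. It may not stay for DAS28-ESR, which is not. State that Week 14 data are included despite the cut-off wording in 4.3.2.
4. In that case, replace the removed tests with descriptive summaries: LY continuers by dose, with the listed Week 12 to Week 24 durability endpoints and a note that continuers are selected on Week 14 response; and SOC participants separately, by randomized arm.
5. If SAP 1.2 stands instead, summarize by randomized sequence.
6. Label any by-arm Week 24 comparison as one of randomized sequences, and state that NRI is not used to turn the planned Week 14 move into placebo nonresponse.

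The cost is SAP wording and fewer models to program. No extra data or participants are needed.

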4.1. Overall Design

This is a Phase 2, proof-of-concept, placebo-controlled, double-blind, randomized study in adult participants with moderately to severely active RA who have had an inadequate response to csDMARDs, or to bDMARDs/tsDMARDs. Participants will be administered LY3462817 or placebo IV Q4W.

Screening Period (Visit 1, Days -42 to -1)

Participants will sign the informed consent document(s) at Visit 1, prior to completion of any procedures. Participants will be evaluated for study eligibility \leq 42 days prior to the baseline visit (Visit 2).

Period 1: Double-blind Treatment (Visits 2 to 6; 12 weeks)

At the baseline visit (Visit 2), participants who fulfill the eligibility criteria will be randomized to receive LY3462817 700 mg, LY3462817 300 mg, or placebo in an allocation ratio of 2:1:1.

The double-blind treatment period will establish the clinical efficacy and safety of LY3462817. The study will be evaluated for the primary objective at the end of the double-blind treatment period.

Period 2 (Visits 6 to 10; 12 weeks)

Data from a Study KDAC interim analysis that includes Week 12 data from participants in the KDAC 700-mg cohort, must be reviewed prior to a participant proceeding to Period 2 in Study KDAD.

At Week 14, participants will be evaluated for clinical benefit.

Participants assigned to LY3462817 at baseline, and achieving low disease activity (CDAI \leq 10) at Week 14 will continue to receive LY3462817 at the randomized dose through Week 24 to assess safety and tolerability and evaluate efficacy.

All other participants at Week 14, regardless of baseline treatment assignment, will stop study drug infusions and should receive standard of care treatment at the investigator's discretion.

Posttreatment Safety Follow-up Period (Visits V801 and 802; 12 weeks)

Following Period 2, participants will be followed posttreatment for 12 weeks to assess safety, study drug exposure, and clinical disease activity measures. Participants who discontinue the study intervention per Section 7 will have their last visit at 12 weeks from the last administration of the study intervention.

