6.5.2. Prohibited Concomitant Therapy

Live vaccinations are not allowed up to 3 months prior to screening or at any time during the study. Live herpes zoster vaccination is not permitted within 30 days of planned randomization or at any time during the study.

Nonlive seasonal vaccinations and/or emergency vaccination, such as rabies or tetanus vaccinations, are allowed.

6.5.3. Standard of Care Therapy after Week 14

All placebo patients should begin SOC therapy at Week 14 at the investigator's discretion.

Participants randomized to LY3462817 at baseline and not achieving low disease activity (CDAI ≤ 10) at Week 14 will no longer receive study drug infusions and should receive SOC therapy at the investigator's discretion.

Participants who achieve low disease activity at Week 14, and maintain treatment with LY3462817 during Period 2, can be switched to SOC prior to Week 24 if the participant stops receiving clinical benefit. Name(s) and dosage regimen(s) must be recorded for the SOC therapy. Standard of care medications will not be supplied by the sponsor.

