4.1. General Considerations

The independent variable, previous RA therapy population, is defined as only csDMARD experienced or bDMARD/tsDMARD experienced participants. Unless otherwise indicated in the statistical analysis plan (SAP), the analyses will be conducted as follows:

Analysis for	Description
Primary and secondary endpoint analyses comparing LY3462817 to placebo	Tested at a 2-sided level of 0.05 for frequentist analyses
Adjustments for multiplicity	None to be performed
Baseline	Defined as the last available value before the first dose of study intervention for both efficacy and safety analyses. In most cases, this value will be what is recorded at the randomization visit (Visit 2).
Change from baseline	Will be calculated as the visit value of interest minus the baseline value.
Efficacy and patient-reported outcome (PRO) analysis	Analysis models may contain the independent variables such as treatment group, baseline disease activity, and previous RA therapy population. Endpoint analyses will use the FAS unless otherwise specified.
Dichotomous responder endpoints	Missing data will be imputed using the nonresponder imputation (NRI) method. Will be analyzed using a logistic regression model with treatment group, baseline disease activity, and previous RA therapy population as model covariates.
NRI analysis	Participants will be considered nonresponders if: 
 • they do not meet all the clinical response criteria • they are noncompliant with concomitant medication rules

	
 • they permanently discontinue study intervention at any time before the end of the treatment period for any reason, or • they are randomized and do not have at least 1 postbaseline observation.
Continuous efficacy endpoints	
Mixed-effects model for repeated measures (MMRM) will be used.
 
The MMRM model will include treatment, strata (previous RA therapy population), baseline value, visit, treatment-by-visit interaction in the model as fixed factors, and patient as a random factor.
 
An unstructured covariance matrix will be used to model the within-subject errors. If this analysis fails to converge, other structures will be tested (in this order: Toeplitz, Autoregressive with heterogeneity, and compound symmetry.).
 
The Kenward-Roger approximation will be used to estimate denominator degrees of freedom. Significance tests will be based on least squares means and Type III tests.

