Participant Disposition	
A detailed description of participant disposition will be provided, including a summary of the number and percentage of participants entered into the study and randomized, and number and percentage of participants who complete the study or discontinue, both overall and by reason for discontinuation. A summary of important protocol deviations will be provided.

Participant Characteristics	
Demographic data are collected and responded to demonstrate that the study population represents the target patient population. A summary of baseline participant characteristics, historical diagnoses, preexisting conditions, and prior therapies will be reported by treatment group using descriptive statistics. Other participant characteristics will be summarized by treatment group as deemed appropriate.

Concomitant Therapy	
Previous and concomitant medications will be summarized by treatment group and will be presented by Anatomical Therapeutic Chemical drug classes using the latest version of the WHO drug dictionary.

Treatment Compliance	No analyses are planned to assess treatment compliance, given that participants will receive study intervention directly from the investigator or designee at the study site, under medical supervision.
----------------------	--

Summary statistics for continuous measures will include sample size, mean, standard deviation, median, minimum, and maximum.

For categorical data, summary statistics will include sample size, frequency, and percentages. Percentages will be rounded to one decimal place. Unless otherwise specified, Fisher's exact test will be used for making treatment comparisons.

All statistical tests of treatment effects will be performed at two-sided significance levels of 0.05 and 0.10, respectively, unless otherwise specified. All p-values will be presented to three decimal places.

The Treatment Period is defined as the combination of Period 1 with double-blind treatment and Period 2.

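### SAP 4.5.7 has no rule for LY responders whose drug the protocol stops at Week 14, so maintained ACR response to Week 24 does not measure durability on LY3462817

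*SAP*

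**What the plan says.** Protocol 4.1 lets LY participants with CDAI of 10 or below at Week 14 continue at their randomised dose through Week 24. For the rest, "All other participants at Week 14, regardless of baseline treatment assignment, will stop study drug infusions". Section 6.5.3 repeats this: LY participants above the threshold "at Week 14 will no longer receive study drug infusions and should receive SOC therapy at the investigator's discretion", and "All placebo patients should begin SOC therapy at Week 14".

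SAP 1.2 describes a different Period 2, in which every subject receives LY3462817. The SAP says it is based on the protocol dated 05AUG2020. The current protocol reports a data cut of 2 September 2020 and a decision of 8 September 2020, so it is a later text.

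SAP 4.5.7 plans that "patients achieving desired responses on ACR20/50/70 at Week 14 and maintain till Week 24 will be summarized by treatment arm at each period 2 visit". It compares each LY dose with placebo by logistic regression and applies nonresponder imputation (NRI) to participants who are non-responders at Week 24 or who discontinued before Week 23. It ends: "For participants who discontinue study intervention and/or receive rescue therapy, post-discontinuation or post-rescue observations will not be included". Under SAP 4.1, NRI covers participants who "permanently discontinue study intervention at any time before the end of the treatment period for any reason", and "The Treatment Period is defined as the combination of Period 1 with double-blind treatment and Period 2". I found no exemption for a stop that the protocol itself directs. Only the exposure summary (SAP 4.6.1) limits Period 2 output to participants who remain on LY.

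**The concern.** Response and continuation are judged on different measures. ACR20/50/70 is a relative improvement (protocol 8.1.3); CDAI of 10 or below is an absolute level (protocol 8.1.10). A participant can be in ACR response at Week 14 and still be taken off drug that day. If that person is then recorded as not maintaining response, the result mixes loss of effect with withdrawal by design. The two doses could then differ in apparent durability only because different shares pass the CDAI threshold. Durability is a stated exploratory objective, and a reader of the Week 24 table could not separate the two causes.

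**Working it through.** **1. The plan's own figure.** The documents give none for this analysis. Their only sample-size figure is power above 80% for the primary endpoint: difference 1.05, SD 1.25, 40 on 700 mg against 20 on placebo. The noncentrality is 1.05 / (1.25 × √(1/40 + 1/20)) = 1.05 / 0.342 = 3.07; with 58 degrees of freedom the power is 85.5%. It reproduces, and this point does not touch it.

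**2. An LY participant in ACR response at Week 14 with CDAI above 10.**
- *Plain reading.* Infusions stop at Week 14, which is before Week 23 and within the Treatment Period. The stop is discontinuation for some reason, later observations are dropped, and NRI gives a failure. The result is the same if only the standard of care counts as rescue: the later data go and the missing response is imputed as a failure.
- *Other reading.* The stop is not discontinuation and standard of care is not rescue. Week 16 to 24 data then stay in and count as maintained response in the LY arm, although the participant is off LY.

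**3. Why the two measures part.** If every CDAI component improves by the same fraction x, CDAI reaches 10 or below only when baseline CDAI is at most 10/(1−x):
- x = 20%: 12.5
- x = 50%: 20
- x = 70%: 33.3

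Entry requires at least 6 swollen and 6 tender joints. If these lie within the 28 counted joints, they contribute 12 at baseline, which leaves 12.5 − 12 = 0.5 for both global scores together in the 20% case. Uniform improvement is an idealisation, but it shows the order: ACR20 is affected most, ACR70 least.

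**4. The ceiling on the plain reading.** Let R be the Week 14 ACR response rate in an arm and f the share of those responders with CDAI above 10. The maintained-response rate in the arm cannot exceed R × (1−f). With assumed R = 50%, 40 participants and 80% true maintenance:

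| f | Ceiling, % of arm | Reported | Without the stop |
|---|---|---|---|
| 20% | 40% (16/40) | 32% | 40% |
| 40% | 30% (12/40) | 24% | 40% |
| 60% | 20% (8/40) | 16% | 40% |
| 80% | 10% (4/40) | 8% | 40% |

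For R from 40% to 60% and f from 20% to 80%, the ceiling runs from 0.4 × 0.2 = 8% to 0.6 × 0.8 = 48% of the arm. Two doses with the same R and the same true maintenance, but f of 40% and 60%, would report 24% and 16%.

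**5. Plausible values of f.** The documents give no CDAI distribution, so this step is assumption only. Simulations with mean baseline CDAI of about 29 to 41, global scores in cm, and mean DAS28-CRP change from −1.1 to −2.0 (the plan assumes −1.80 for 700 mg) put CDAI above 10 in:
- 51% to 79% of ACR20 responders
- 18% to 47% of ACR50 responders
- 1% to 5% of ACR70 responders

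With the global scores added in mm, as protocol 8.1.10 and SAP 4.4.1.2.7 read, the ACR20 share is 87% to 95%. For DAS28-CRP low disease activity it is 8% to 11%.

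**6. Placebo.** All placebo participants stop at Week 14, so on the plain reading maintained response after that visit is 0/20 by rule. Against 0/20, 8/40 on 700 mg gives Fisher p = 0.043 and 5/20 on 300 mg gives p = 0.047, whatever the course on placebo would have been. With an empty cell, the planned logistic model has separation.

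**The case against.** The best counter-argument is that the plain reading is not the only one. Protocol 7.1.2 does not list the Week 14 CDAI stop among its criteria for permanent discontinuation, and calls such discontinuation rare. Early permanent discontinuation leads to early-termination procedures (7.1), whereas the schedule of activities only withholds the infusion at Weeks 16 to 24. Standard of care is not clearly a breach of the concomitant-medication rules, because 6.5.1 covers Period 1 and those who remain on LY. The SAP does not define rescue, and the protocol's composite-responder estimand is headed for the double-blind period. This stands: a reader might infer that the SAP certainly scores these responders as failures, and the documents do not settle that. It does not remove the problem, because the alternative credits LY with response on standard of care.

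A reader might also infer a known ceiling, or that a fully durable drug would be seen to lose most of its responders. The documents do not support a figure. SAP 4.5.7 reports by arm and names no denominator of Week 14 responders, and the responder shares in step 5 rest on assumed inputs. A majority appears only for ACR20.

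Finally, the analysis is exploratory. The protocol's own durability endpoint is low disease activity or remission at Week 12 kept through Week 24, and its CDAI version largely agrees with the stopping rule. That limits the weight of the point.

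**Conclusion.** The point holds as a gap between the SAP's Period 2 analyses and the current protocol. SAP 4.5.7 carries no allowance for a protocol-directed stop, which fits the Period 2 described in SAP 1.2 but not protocol 4.1 and 6.5.3. On neither reading does the maintained ACR response measure durability on LY. On the plain reading the arm-level percentage is capped at the share that both responds and has CDAI of 10 or below at Week 14, and doses can differ through CDAI pass rates alone. That cap follows from the wording; its size does not. The statement that about half or more of ACR20 responders, a minority of ACR50 and few ACR70 responders are affected depends on the assumed baseline CDAI, effect size and global-score units. The same scoring reaches the Period 2 low disease activity and remission summaries on DAS28-CRP, DAS28-ESR and SDAI; for DAS28-CRP low disease activity the assumed-input effect is smaller. The Week 12 primary analysis is unaffected, and nothing here implies that the stopping rule is wrong. The change should be made, but it is not critical.

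**What to change.** - Reconcile SAP 1.2 and the Period 2 analyses with protocol 4.1 and 6.5.3, and state whether the Week 14 stop counts as discontinuation and standard of care as rescue.
- In SAP 4.5.7, and in Period 2 maintenance summaries on measures other than CDAI low disease activity, report maintenance descriptively by LY dose among Week 14 responders who continued LY3462817.
- Report Week 14 responders stopped under the protocol rule as a separate count, not imputed as failures.
- Keep NRI for participants who continued and later stopped or switched.
- Replace the LY-versus-placebo logistic test of maintenance with this summary, because no placebo participant continues.
- State that the denominator is small and selected after randomisation, so dose comparisons within it are not randomised comparisons.

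The clinical stopping rule is not changed. The cost is SAP wording, one more row per table and the loss of a test that could not be interpreted. Precision will be low: with an assumed CDAI pass rate of 21% to 33%, at most about 4 to 7 of 20 on 300 mg (20 × 0.21 = 4.2; 20 × 0.33 = 6.6) and 8 to 13 of 40 on 700 mg (40 × 0.21 = 8.4; 40 × 0.33 = 13.2) would be in the denominator.
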